The two-site study takes place at clinical programs at US children's hospitals: the UW and UCLA Pediatric Complex Care Programs were each established to deliver care to children with medical complexity. Each program is comprised of primary care providers, care coordinators, and extended visit lengths, deliver comprehensive care to children with cerebral palsy. These sites have existing collaborative relationships through their participation in the CYSHCNet national research network (<http://cyshcnet.org>) and other federally funded initiatives, and a track record of successful productive scientific collaboration.

Description of Study Intervention/Experimental Manipulation: The study period will be divided into three waves: after each wave, feasibility, acceptability, and fidelity data will be reviewed against pre-defined measures of success to adjust the protocol and overcome implementation barriers.

This study will be conducted through a six-month randomized pilot trial. Briefly, after recruitment and baseline assessments, eligible caregiver/child dyads are randomized to intervention (I) or active control (AC). Intervention subjects receive respiratory illness action plans and weekly mobile health (mHealth) confidence surveillance. At times of low confidence or hospitalization, just-in-time action planning and coaching activities are conducted. AC subjects will receive usual comprehensive medical care and coordination. Assessments of feasibility, acceptability and fidelity, as well as clinical outcomes, will be conducted at baseline and monthly intervals for 6 months. Intervention outcomes will be evaluated at baseline (i.e., randomization) and 6 months post-enrollment, and will also include the primary clinical outcome (i.e., hospitalization for respiratory diagnosis).

[figure not shown]
Study Duration*:

24 months

Participant Duration:

6 months

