2.2 BACKGROUND

Cerebral palsy (CP) is the leading cause of motor disability in childhood^{8,9} and has grave respiratory consequences.¹³ CP is caused by damage to the developing brain that permanently disrupts the ability to

control movement and maintain posture. Children with severe CP have spastic quadriplegia (i.e., all four extremities affected) and level V gross motor function classification system [GMFCS] (i.e., no independent mobility). Mechanisms of respiratory illness in severe CP parallel those of other neuromuscular diseases,²⁷ examples include respiratory muscle weakness, recurrent infections and aspiration with inflammatory fibrosis, impaired airway clearance from altered tone, upper airway abnormalities and poor chest wall compliance.^{28,29} CDC estimates >\$16B in lifetime cost for the children with CP born in 2000 alone.¹⁰

Respiratory illness is consistently the #1 cause of death and hospitalization in severe CP.^{4,30} Only 33% of children with CP and four co-occurring disabilities survive to age 30.³¹ Respiratory illness accounts for 59% of deaths^{3,4} and 25% of hospitalizations^{1,7,8} in severe CP. Moreover, respiratory illness strongly predicts future episodes; respiratory hospitalization risk is 10-fold higher with a respiratory illness in the past year.¹⁴ In fact, over 20% of hospitalizations are followed by another within 30 days and nearly 70% in the next year.⁷ Hospitalizations for respiratory illness are 76% costlier⁸ and 2.5 times longer for children with severe CP than those without.¹⁴ Prevention of these events is a significant need, and a key to improving quality of life and mortality.^{6,13} Though the respiratory illness risk factors in severe CP are considered modifiable,¹⁴ and despite investments in respiratory care, little improvement in these outcomes has occurred in CP in 40 years.^{1,2,8}

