RCT participants in both groups will undergo assessments of demographic, clinical and caregiving measures reported through questionnaire and medical record review at baseline at 6 months after enrollment. Feasibility, acceptability and fidelity data will be collected through parent-report, medical record review, and research team logs monthly during the intervention, and, for control group participants, at 6 months after enrollment.

Data about research participants (children and their families) will be collected by study research assistants through electronic self-administered questionnaires or structured interviews with parents either over the phone or in person, abstraction of child medical record data by the study RAs, and (for intervention group families) through phone interactions and direct observation with health coaches in RE-PACT. Content of these assessments include parent-report questions about child and parent health, parent perceptions of child health, family socio-demographic information, care utilization, and experiences of caregiving.

Analyses will assess feasibility, acceptability, fidelity and effect size estimates (by comparing numbers of respiratory exacerbations between intervention and usual care groups). We will use pre-specified definitions of success for each of our feasibility, acceptability and fidelity measures. We anticipate being underpowered to assess the efficacy of the intervention in this pilot study, but to inform a future large RCT we will test differences between intervention and active groups in the primary and secondary clinical outcomes. For each of these measures, we will compare differences between intervention and active control group outcomes at 6 months controlling for their baselines. While we anticipate that the intervention and control groups will be similar due to random assignment, we will adjust for any variables in our analysis that are not equal between the groups given the small sample size. In addition, we will analyze for any effect of primary home language on the study outcomes, as this may affect families’ ability to navigate systems of care in the U.S. To explore theoretical intervention mechanisms, we will also test the mediating effect of caregiver capability, opportunity, and motivation measures on the relationship between intervention and respiratory illness outcomes.

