Primary Study Endpoints - Feasibility, Acceptability, Fidelity: The specific measures and pre-specified definitions of success are listed in **Section 3**. These measures will be summarized between each of the three waves with protocol adjustments made for any measures below the definition of success.

Clinical Endpoints:

- Primary clinical outcome is severe respiratory illness, defined as respiratory diagnosis requiring hospitalization. Respiratory diagnosis includes discharge diagnosis of any of the following: asthma, pneumonia

(community or hospital acquired), bronchiolitis, influenza, upper or lower respiratory tract infection, tracheitis, aspiration pneumonia/pneumonitis, chronic lung disease, respiratory failure.¹²⁰ Field-testing assessment of this endpoint with trained research personnel at study sites demonstrated inter-rater reliability (Kappa) > 0.9.

- Secondary outcomes include: total hospital days during severe respiratory illness, numbers of systemic steroid courses, systemic antibiotic courses, respiratory ED visits, and death. Systemic corticosteroid course is defined by oral or parenteral corticosteroid prescribed for respiratory diagnosis, including hydrocortisone, prednisone, prednisolone, or methylprednisolone at least 1 mg/kg/day (or 30 mg/day) x minimum 3 days, or dexamethasone at least 0.15 mg/kg/day (or 10 mg/day) x 1 or more days. Physiologic or stress replacement doses in adrenal insufficiency are excluded. Systemic antibiotic course is defined by oral or parenteral antibiotics prescribed for respiratory diagnosis x minimum 3 days. The specific antibiotics are derived from IDSA pediatric pneumonia guidelines¹²¹ and published literature.¹²² Respiratory ED visits are any ED visits not resulting in admission and have a discharge respiratory diagnosis.

Additional Assessment Measures:

MEASURES	SOURCE	MEASURE DETAIL
Covariates		
Child and Caregiver Demographics	Survey	Child: age, gender, primary language, race/ethnicity, payer, family structure Caregiver: relationship, age, gender, language, race/ethnicity, education, health literacy, ¹¹⁴ income, rurality
Confounders		
Child Clinical Characteristics	Electronic health record	Organ systems affected by chronic conditions, subspecialists in past year, medical technologies used (e.g., tracheostomy, gastrostomy, etc.), duration of enrollment clinical program, numbers of ED visits and hospitalizations in past year, and respiratory treatments at time of enrollment (medications and devices)

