Caregiver Strain	Survey	Caregiver Strain Questionnaire (CGSQ); ¹¹⁵ – mean global, objective, subjective scale scores Mental health (PHQ2) ¹¹⁶
Theory / Mechanism		
Capability	Survey	Family Caregiver Activation in Transition Measure (FCAT) ¹¹⁷ – mean composite score Caregiver General Self-Efficacy Scale (GSES) ¹¹⁸ – mean composite score
Opportunity	Survey	Family Experiences with Care Coordination (FECC) ¹¹⁹ - % top-box score for selected items
Motivation	Text logs	Confidence Responses mHealth texting (weekly score 1 through 10)

Assessment Procedures. Feasibility, acceptability and fidelity endpoint data will be collected during each of the three waves by research personnel reviewing study logs, conducting monthly chart reviews, and

administering surveys (by telephone, in person, or sending electronic self-administered links) with caregivers randomized to intervention. For active control groups participants, feasibility of assessments will be evaluated by completion rates at study exit. Caregiver and child measures above will be recorded at baseline, endpoints will be recorded at study exit (6 months after T0). Caregiving measures, which may change as a result of the intervention, will be collected at baseline and study exit. In addition, intervention and active control caregivers will be debriefed at study exit on their experiences in the study, and asked for feedback on the strengths, weaknesses and any concerns about the protocol. Between each wave and after the third wave, clinical teams at each site will be debriefed on strengths, weaknesses, and concerns about the protocol.

Reliability of Assessment Measures. The CP GMFCS measures and all the caregiving measures have been well-documented as reliable in the literature.^{11,74,115-119} We have separately established the reliability of identifying respiratory illnesses in our preliminary research (Kappa > 0.9). We will ensure reliability in data collection through direct observation, data auditing, establishing clear data dictionaries / definitions, using uniform variable definitions, and a central data repository coordinated and maintained by UW.

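### No respiratory-specific baseline or look-back is listed for any clinical endpoint, although Section 4.1 promises to control for baselines, and the sections disagree on when clinical outcomes are measured

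*Combined protocol and SAP*

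**What the plan says.** **Timing of the clinical endpoints.** Section 8.1 (Assessment Procedures) takes caregiver and child measures at baseline, states that "endpoints will be recorded at study exit (6 months after T0", and collects caregiving measures at both times. The synopsis (1.1) differs: "Assessments of feasibility, acceptability and fidelity, as well as clinical outcomes, will be conducted at baseline and monthly intervals for 6 months". It adds that "Intervention outcomes will be evaluated at baseline (i.e., randomization) and 6 months post-enrollment, and will also include the primary clinical outcome".

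**Baseline content.** Section 4.1 says that "RCT participants in both groups will undergo assessments of demographic, clinical and caregiving measures reported through questionnaire and medical record review at baseline" and again at 6 months. The content of that record review appears only in the Section 8.1 table. Its utilization item is "numbers of ED visits and hospitalizations in past year", with no respiratory split. The table also lists medical technologies and respiratory treatments at enrollment.

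**Planned adjustment.** For the clinical outcomes, Section 4.1 promises that "we will compare differences between intervention and active control group outcomes at 6 months controlling for their baselines". The primary NB model in Section 9.4.3 has study arm as its only predictor, with site as stratification factor. A secondary NB model selects covariates by penalized regression from clinical and demographic characteristics.

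**Monthly data.** Sections 9.1 and 9.4.3 model monthly presence or absence of severe respiratory illness. Section 9.4.3 does the same for steroid courses, antibiotic courses and respiratory ED visits. The schedule (1.3) puts monthly study assessments under the intervention arm only, and Section 5.5 limits monthly contact to intervention subjects.

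**Stated predictor.** Section 2.2 reports that "respiratory hospitalization risk is 10-fold higher with a respiratory illness in the past year" and puts respiratory illness at 25% of hospitalizations in severe CP.

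**The concern.** The clinical endpoints, apart from death, are respiratory-specific counts or days. A count has no value at the moment of randomisation. It needs a look-back window, and none is given for any of them. Controlling for baseline therefore has no named variable, and the primary model has no term in which to put one.

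Analysis alone cannot repair this. Section 9.3 adjusts for variables that turn out unequal between the arms, Section 9.4.5 compares the measures listed in Section 8.1, and the penalized model selects among recorded characteristics. All three work only on what was collected. A chance imbalance in past respiratory illness could go unseen and uncorrected.

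What is at stake is the pilot's effect-size estimate, which Sections 9.2 and 9.4.3 say will be used to size the later trial. With about 40 evaluable children per arm, a strong prognostic factor affects both its precision and its exposure to chance imbalance.

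**Working it through.** **Plan's own figure.** The plan gives no figure for the value of baseline adjustment. Its power table (9.2) supplies inputs only. The usual NB Wald formula does not reproduce that table: for RR 3 and 0.02 events per patient-month it gives 49%, where the table as extracted shows 19%. The table's columns may have shifted in extraction. That is a separate matter. The main result below is a ratio of variances and does not use the table's cells.

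**Inputs from the documents.** One severe respiratory illness per child-year, so μ = 0.5 per 6 months (9.2). Overdispersion φ = 1.0 (9.2). 45 per arm with up to 10% missing, 45 × 0.9 = 40.5, taken as 40 (9.2). A 10-fold contrast (2.2), treated as a rate ratio.

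**Assumptions not in the documents.** The proportion p of children with a past-year respiratory illness; that the 10-fold contrast holds in this sample; that the total φ of 1.0 includes it; equal rates in the two arms.

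**Unadjusted.** Var(log RR) = 2(1/μ + φ)/n = 2(2 + 1)/40 = 0.150.

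**Adjusted.** Two groups have rates in the ratio 10:1 and overall mean 0.5.
- Low rate = 0.5/(1 + 9p); high rate = 10 × low rate.
- CV² = 81p(1 − p)/(1 + 9p)².
- Residual φ = 2/(1 + CV²) − 1.
- Within a stratum of n_s children per arm and mean μ_s, the information is n_s/[2(1/μ_s + residual φ)]. Add the two strata and invert.

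*p = 0.5.* Rates 0.0909 and 0.909; CV² = 20.25/30.25 = 0.669; residual φ = 0.198. Information = 20/[2(11 + 0.198)] + 20/[2(1.1 + 0.198)] = 0.893 + 7.704 = 8.597. Variance 0.1163, a reduction of 22%. Since 0.150/0.1163 = 1.29, this equals 29% more children.

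*p = 0.7.* Rates 0.0685 and 0.685; CV² = 17.01/53.29 = 0.319; residual φ = 0.516. Information = 12/[2(14.6 + 0.516)] + 28/[2(1.46 + 0.516)] = 0.397 + 7.085 = 7.482. Variance 0.1337, a reduction of 11%, equal to 12% more children.

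**Limit of the inputs.** At p = 0.3, CV² = 17.01/13.69 = 1.24, which exceeds the total φ of 1.0 and makes the residual φ negative (−0.11). A 10-fold contrast and a total φ of 1.0 cannot both hold below about p = 0.37, so no gain is quoted there. At p = 0.4, near that limit, the variance is 0.104 (31% lower).

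**Weaker contrast.** With 3-fold (an assumption), the same steps give 0.136 at p = 0.5 (residual φ 0.60; 9% lower) and 0.142 at p = 0.7 (residual φ 0.75; 5% lower).

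**Power.** For illustration, take the 40% lower rate reported for the earlier PACT trial (2.2): means 0.5 and 0.3, 40.5 per arm. Unadjusted variance = (2 + 1 + 3.33 + 1)/40.5 = 0.181, SE 0.426, power 22%. Adjusted for the 10-fold predictor with p from 0.4 to 0.7: SE 0.368 to 0.406, power 28% to 24%.

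**Chance imbalance.** With 45 per arm, the difference in prevalence between arms has SD d = √[2p(1 − p)/45]. A one-SD imbalance multiplies the unadjusted RR by [1 + 9(p + d/2)]/[1 + 9(p − d/2)]. At p = 0.5, d = 0.105 and the factor is 5.974/5.026 = 1.19. Over p = 0.4 to 0.7 it runs from 1.23 to 1.13.

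**The case against.** A reader of Section 8.1 alone might infer that no baseline exists for the clinical outcomes, or that they are recorded only at exit. The documents do not support either. The synopsis places clinical outcomes at baseline and monthly, Section 4.1 has record review at baseline in both arms, and Section 9.4.3 presupposes monthly outcome data. What is shown is a contradiction and an undefined look-back, not an absence. Likewise, the past-year counts are unqualified; calling them all-cause is a reading. The case report form and data dictionaries are not in the documents, so one cannot say that the variables will be missing from the database.

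The information is also recoverable. Consent covers the child's medical record, past-year hospitalizations are already abstracted, and discharge diagnosis defines the endpoint. This stands, and it is why the fix is cheap.

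The size can fairly be called favourable. The comparison is with no adjustment at all, while covariates already listed (general utilization, technologies, respiratory treatments) may carry part of the signal. The 10-fold figure is a background citation, and this sample is restricted to children with respiratory care needs. For the same reason, the 25% share may understate how much of their hospital use is respiratory, so the unqualified count could be a better proxy than that share suggests. All of this stands and limits the claim.

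Finally, the primary outcomes are feasibility, acceptability and fidelity, and the plan admits that it is underpowered for efficacy. That lowers the priority. It does not remove the point, because effect-size estimation is the stated secondary objective.

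**Conclusion.** The point holds as a contradiction between sections plus an omission from the listed measures. Section 4.1 promises baseline control that Section 8.1 gives no respiratory variable for and that the primary model in Section 9.4.3 does not carry. The predictor that the background singles out is not a listed item. The monthly models also lack a matching assessment schedule in the control arm.

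The precision gain from closing the gap is modest: Var(log RR) is lower by 22% at 50% prevalence and by 11% at 70%. This rests on an assumed prevalence, a 10-fold contrast that applies to this sample, mean 0.5 per 6 months, total φ of 1.0 and 40 per arm. It shrinks if the contrast is weaker or if covariates already collected carry part of it. Protection against chance imbalance is the second benefit: under the same contrast, a one-SD imbalance shifts the unadjusted RR by a factor of about 1.13 to 1.23. The change is worth making because it is cheap and serves the estimate that the pilot is meant to deliver.

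**What to change.** 1. Reconcile the synopsis and Sections 1.3, 4.1, 5.5, 8.1, 9.1 and 9.4.3 on whether and when clinical outcomes are measured at baseline and monthly, and in which arms. If the monthly models are kept, state how control-arm monthly data are obtained.
2. In both arms, extend the baseline record abstraction to the 12 months before randomisation, using the exit definitions: severe respiratory illnesses, their hospital days, respiratory ED visits, systemic steroid courses and systemic antibiotic courses. For children under 1 year, record the shorter window. Death needs no baseline.
3. Abstract the look-back retrospectively for any wave already enrolled.
4. Pre-specify the prior-year count of the same outcome, for example as log(count + 1), as a covariate alongside arm and site in each NB model. The calculation above used a yes/no predictor, so it indicates the gain from this covariate only approximately.

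The cost is some extra chart time per child and a case report form change. The definitions, the abstraction process and the staff are already in the plan.

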Tertiary/Exploratory			
To explore the mediating relationships between RE-PACT and capability, opportunity, motivation (COM-B) measures.	Capability : Family Caregiver Activation in Transition Measure (FCAT)117 – mean composite score Caregiver General Self-Efficacy Scale (GSES) 118 – mean composite score. Opportunity : Family Experiences with Care Coordination (FECC)119 - % top-box score for selected items Motivation : Confidence Responses mHealth texting (weekly score 1 through 10)	Blending our foundational research on preventing hospitalizations, ^{38,39} with behavioral intervention theory, ¹¹³ our conceptual model suggests that decisions to seek care (behaviors) are influenced by capability (family capacity), opportunity (health system and susceptibility), and motivation (confidence). Confidence is a modifiable expression of self-efficacy to achieve an outcome, i.e., to avoid hospitalization and manage (respiratory) crisis at home.	A theorized mechanism of RE-PACT's effect is that the combination of action planning, mHealth surveillance, and coaching, will increase caregiver capability, opportunity, motivation to manage respiratory illness in severe CP.

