6 STUDY INTERVENTION(S) OR EXPERIMENTAL MANIPULATION(S)

6.1 STUDY INTERVENTION(S) OR EXPERIMENTAL MANIPULATION(S) ADMINISTRATION

6.1.1 STUDY INTERVENTION OR EXPERIMENTAL MANIPULATION DESCRIPTION

The Respiratory Exacerbation Plans for Action and Care Transitions (RE-PACT) intervention has three primary activities: (1) mHealth surveillance of parent confidence to avoid hospitalization, (2) respiratory illness action planning, and (3) just-in-time adaptive coaching response triggered by low confidence or hospitalization. The theoretical basis of the intervention includes efficacy of the initial PACT trial, and prior research on preventing hospitalizations combined with behavioral intervention theory which suggests that decisions to seek care (behaviors) are influenced by capability (family capacity), opportunity (health system and susceptibility), and motivation (confidence). Confidence is a modifiable expression of self-efficacy to achieve an outcome, i.e., to avoid hospitalization and manage (respiratory) crisis at home. In our earlier work, low confidence predicted hospitalization.

Participants randomized into the intervention will receive initial T_0 intervention activities (mHealth monitoring and respiratory action plan) by phone, at clinic, or during a hospitalization within one month of enrollment.

mHealth surveillance. Upon enrollment, families will begin receiving weekly text messages asking them to rate their confidence (1-10) for their child to avoid a hospitalization in the next month.

Action Planning. The action and format are adapted from the original PACT study, and contents include (at minimum) recognizing, describing and managing the child's known contributors to respiratory illness. In step 1, objective and subjective indicators of baseline ("green"), concerning ("yellow"), and severe ("red") statuses are defined (e.g., >2 L/min of oxygen). In step 2, the specific actions caregivers should take to manage each status are defined (e.g., increase vest, albuterol, suction to q4, use oxygen up to 4 L/min).

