9.4.3 ANALYSIS OF THE SECONDARY ENDPOINT(S)

Clinical Outcomes. We will test differences between treatment (intervention or control) groups in the primary and secondary respiratory illness outcomes. Our goal with these analyses is to estimate effect sizes for the differences between groups which will allow precise sample size calculations for a future large-scale trial.

Primary clinical outcome is the severe respiratory illness rate, defined as the total number of severe respiratory illnesses divided by the person-months over the 6-month follow-up period. The severe respiratory illness rate will be analyzed using a negative binomial (NB) regression model to account for overdispersion in the count data. For the primary analysis, univariate NB regression analysis will be conducted with study arm as a predictor variable. Study site will be included as a stratification factor in the primary analysis to account for stratified randomization. The observed effect size of the analysis will be quantified in terms of relative risk (RR) and reported along with the corresponding 95% confidence interval.

As a secondary analysis, multivariate NB regression analysis will be performed to compare the severe respiratory illness rates between study arms. In this analysis, clinical and demographic characteristics will be included as covariates in an initial non-parsimonious model. The least absolute shrinkage and selection operator (lasso) and elastic net penalty methods for negative binomial regression models will be utilized to identify a parsimonious model with independent covariates. These methods are considered state-of-the art techniques for variable selection (Wang Z., et al. Stat Methods Med Res. 2016).

Longitudinal changes in the severe respiratory illnesses within and between study arms, will be evaluated with generalized linear mixed effects model with a logit link function and subject specific random effects. An autoregressive (AR) correlation structure will be utilized to account for within subject correlations. In this analysis, the presence/absence of severe respiratory illness at the monthly assessments will be the dependent variable, study arm will be included as a predictor variable and study site as a stratification variable to account for the stratified randomization.

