9.4.9 EXPLORATORY ANALYSES

We will test the mediating effect of caregiver capability, opportunity, and motivation (COM-B) measures on the relationship between intervention and respiratory illness outcomes. The mediating effects will be evaluated by conducting a multi-step analysis approach. In the initial step, NB regression analyses will be conducted to examine whether there are differences in respiratory illness outcomes (number of severe respiratory illnesses, systemic steroid courses, systemic antibiotic courses, and respiratory ED visits) between the intervention and control arm, as described in the previous section. In the next step, we will conduct a sequence of univariate analyses, by regressing each potential mediator variable (caregiver capability, opportunity, and COM-B) on the binary study arm variable. If significant associations between the potential mediator variables and study arm are detected, we will regress the respiratory illness outcomes on both the mediator variables and study arm indicator variable using ANCOVA. The

mediation effect for each potential mediator variables will then be tested using the Sobel z-test based on the slope parameter estimates from the corresponding regression models.

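### Capability and opportunity scores are taken only at baseline and exit, so the exploratory Sobel analysis cannot establish temporally ordered mediation and can report effects of illness on the score as mediation

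*Combined protocol and SAP*

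**What the plan says.** The tertiary objective in section 3 is "To explore the mediating relationships between RE-PACT and capability, opportunity, motivation (COM-B) measures". Capability is measured by FCAT and GSES, opportunity by FECC, and motivation by the weekly text score.

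Timing is given twice. Section 8.1 (Assessment Procedures) says "Caregiving measures, which may change as a result of the intervention, will be collected at baseline and study exit". Section 4.1, for both arms, refers to "caregiving measures reported through questionnaire and medical record review at baseline at 6 months after enrollment". FCAT, GSES and FECC belong to this group: section 8.1 also says "The CP GMFCS measures and all the caregiving measures have been well-documented as reliable in the literature", and the references cited there include the three scales (117 to 119). Baseline assessment and randomization share the enrollment visit (section 1.3).

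The primary clinical outcome in section 9.4.3 is a rate, "defined as the total number of severe respiratory illnesses divided by the person-months over the 6-month follow-up period".

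Section 9.4.9 regresses each mediator on study arm. Where that association is significant, it regresses the illness outcomes on mediator and arm. Then: "The mediation effect for each potential mediator variables will then be tested using the Sobel z-test". It names no mediator time point, no lag and no adjustment for the baseline score.

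**The concern.** Mediation means that the intervention changes the score and the changed score then alters illness. A baseline score taken at the randomization visit cannot carry an intervention effect, so the exit score is the only candidate mediator value, and no counted illness comes after it. The slope of illness on exit score cannot separate score affecting illness from illness affecting score. The second direction is plausible: a child's admission may change a caregiver's self-efficacy or view of care coordination.

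There may also be a path of opposite sign. Section 6.1.1 describes a "just-in-time adaptive coaching response triggered by low confidence or hospitalization". If an admission leads to coaching in the intervention arm, and coaching raises the score, illness would be associated with a higher exit score.

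What is at stake is an unsupported statement about mechanism, made in a trial whose theory rests on these pathways.

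**Working it through.** The documents give no power or error rate for the mediation analysis, so there is no planned figure to reproduce.

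**Step 1: order of measurement.**
- Baseline score: at the randomization visit, before any intervention.
- Illness count: from then to month 6.
- Second and last score: at the month-6 exit.
- Interim scores: none scheduled in either arm. Monthly contacts are for intervention subjects only (section 5.5), and section 8.1 ties the intervention-arm data collection to feasibility, acceptability and fidelity.

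**Step 2: can the planned test be falsely positive?** The steps of section 9.4.9 were simulated with the mediator having no effect on illness.

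Inputs from the documents:
- 45 per arm with 10% missing (section 9.2): 45 × 0.9 = 40.5, taken as 41.
- One severe illness per year (section 9.2): control mean 1 × 6/12 = 0.5 over 6 months.
- Negative binomial overdispersion 1.0 (section 9.2).
- Intervention-to-control rate ratio 0.6, from the 40% reduction quoted for the earlier PACT trial (section 2.2): intervention mean 0.5 × 0.6 = 0.3.
- Two-sided 0.05 level (section 9.4.1).

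Assumptions not in the documents: the intervention raises the exit score by 0 to 0.8 SD, and having any admission lowers it by 0, 0.5 or 1.0 SD.

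Procedure: least squares of exit score on arm gives slope *a* with standard error *s_a*; stop unless p < 0.05. Least squares of illness count on arm and score gives score slope *b* with standard error *s_b*. Then z = *ab* / √(*a*²*s_b*² + *b*²*s_a*²), significant if |z| > 1.96.

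False Sobel significance:

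| Arm effect on score | Admission lowers score 0.5 SD | Admission lowers score 1.0 SD |
|---|---|---|
| 0.8 SD | 24% | 75% |
| 0.5 SD | 10% | 43% |
| 0.3 SD | 4% | 19% |
| 0 | 0.3% | 2% |

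With no effect of admission on the score and a 0.8 SD arm effect, the rate is about 2%. The excess therefore comes from the reverse effect. At 0.8 SD the significance gate is passed in about 95% of trials, so it gives no protection.

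**Step 3: sensitivity to coding.** If each illness, rather than any admission, lowers the score, the rates rise. With a 0.8 SD arm effect, a drop of 0.3 SD per illness gives about 36% and 0.5 SD about 73%.

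**Step 4: does baseline adjustment repair it?** No. With 40 per arm, a 0.5 SD arm effect, a 0.5 SD drop per illness, the same rate ratio and an assumed baseline-to-follow-up correlation of 0.6, the false rate is 42% unadjusted and 71% adjusted. Adjustment removes noise but leaves the order unchanged.

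**Step 5: the coaching path.** If an admission does not lower the score but post-admission coaching raises it by 0.8 SD in the intervention arm, the test is significant in about 13% of trials, nearly all with the wrong sign.

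**Step 6: scores at month 3.** Scores were taken at month 3, illnesses counted in months 4 to 6, with adjustment for baseline score and months 1 to 3 illness. The false rate is about 4% or less. Expected illnesses left are 41 × 0.25 + 41 × 0.25 × 0.6 = 10.25 + 6.15 = 16.4. Even if the whole rate ratio of 0.6 ran through the score, power was only about 15% to 31% (arm effect 0.3 to 0.8 SD, correlation 0.6 assumed).

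**The case against.** The objective is only to explore, and it sits in the tertiary tier of a pilot that declares itself underpowered for efficacy. A reader might infer that it cannot be answered at all. The documents do not support that: the randomized comparison of exit scores and the association between score and illness both remain estimable. Only the ordered, causal reading is lost.

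A reader might also infer that a spurious result would mislead the design of the later trial. The documents say that trial will draw on feasibility data and clinical effect sizes (sections 4.1, 9.2, 9.4.3). None says that the mediation output sets any feature of it.

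The simulated rates rest on assumed shifts. When the intervention does not itself move the score, the rate stays at 2% or below in the scenarios tabulated. They show what can happen, not what is likely. This stands, and is why a range is given.

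The wrong-sign case uses one side of a contradiction. The synopsis and sections 3 and 6.1.1 make hospitalization a coaching trigger; section 4.2 says coaching is triggered only by text responses. Those passages must be reconciled. The main path, illness lowering the score, does not depend on them.

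None of this supplies an interim score or an ordering safeguard. The weekly motivation score does not fill the gap, because section 4.2 sets up texting only in the intervention arm.

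**Conclusion.** The concern holds in a limited form. As scheduled, FCAT, GSES and FECC cannot support temporally ordered mediation, and the Sobel analysis can report illness-to-score effects as mediation. The ordering defect follows from the documents alone. Its size does not: false significance runs from 0.3% to 75% in the table above, driven mainly by how far the intervention moves the exit score and how far an admission lowers it. The 13% wrong-sign figure applies only if hospitalization triggers coaching. Primary and secondary results are untouched. The change is still worth making because it is nearly free and prevents an unsupported conclusion.

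**What to change.** **Preferred.** In sections 9.1 and 9.4.9, delete the Sobel mediation test for FCAT, GSES and FECC. Report instead the between-arm difference in each exit score, adjusted for its baseline value, and the association between exit score and illness, with a statement that neither shows mediation. The cost is wording and a weaker claim about mechanism.

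**Optional, if ordered mediation is wanted.** Send the three scales once by REDCap survey at month 3 in both arms. Analyse those scores against illnesses in months 4 to 6, adjusting for baseline score and months 1 to 3 illness. This controls the false rate, but it adds a contact for controls, who under section 6.1.1 complete only assessments before and after the study. It also leaves about 16 illnesses, with the low power shown above. The choice has to be made before the month-3 visits, because the timing cannot be repaired afterwards.

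**Separately,** reconcile the synopsis and sections 3 and 6.1.1 with section 4.2 on whether hospitalization triggers coaching.
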